6.4 DISPOSITION OF SUBJECTS AND WITHDRAWALS

All subjects who provide written informed consent will be accounted for. The frequency and percentage of subjects who complete each scheduled assessment will be summarized in a tabular format including details on study exits with reason for exit.

6.5 PROTOCOL DEVIATIONS

Major protocol deviations will be summarized. This summary will include the number and percent of subjects with each major deviation type. A major protocol deviation is defined as a subject enrolled and treated, but who subsequently does not meet inclusion criteria or does meet exclusion criteria or have other deviations determined to impact the primary efficacy or safety endpoints analyses for this trial. Additionally, all protocol deviations, major and minor, will be

summarized. This summary will include the number and percent of subjects with each protocol deviation) and reason within each time interval.

6.6 MISSING DATA IMPUTATIONS

No safety data will be imputed whereas efficacy data may be imputed based on subject-specific situations. Regarding efficacy, for any subjects missing 12-month clinical, neurological and angiographic evaluations, the most likely 12-month efficacy outcomes at the subject-level will be imputed. For this purpose, all available 12-month data will be included. Additionally, for subjects not reporting 12-month occlusion data, results may be imputed from 6-month occlusion data along with available pre-treatment data. Safety data will not be imputed; 12-month contact will be sought to confirm stroke and survival status to confirm safety success. Subjects with no follow-up data will not be imputed for analysis of the primary effectiveness endpoint but alternative source-document verified data will be considered in judging 12-month efficacy.

In the event such imputations for the subjects with missing 12-month data cannot be made, then the other subjects with completed 6-month and 12-month safety and efficacy outcomes will be used to compute the respective probabilities of 12-month efficacy outcomes conditional on 6 month outcomes for the respective ITT, Safety, and PP populations.

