For efficacy, if the one-sided 95% lower credible interval is at least 45%, then efficacy is established. For safety, if the one-sided 95% upper credible interval is no more than 25%, then safety is established. Bayes logistic models will be used to compute the credible intervals controlling for age (<55, 55-64, ≥65) gender (male, female), zone (1, 2, 3), and region (Japan vs others). If both the safety and effectiveness null hypotheses are rejected, then the study goal will be considered to be met.

The primary effectiveness endpoint is defined, such that a subject will be considered a failure if the following occurs:

- A retreatment of the target aneurysm is required at any time prior to the 12-month follow-up evaluation, failure is considered to have occurred at the time of retreatment;
- The study device is deployed and properly positioned at the target site but fails to fully occlude the aneurysm by 12 months post-procedure;

Or if

- Presence of >50% stenosis of the parent artery at the target aneurysm at 12 months.

If a subject is a failure of this endpoint for multiple elements of the composite endpoint, then the subject is treated as a failure at the time of the earliest failure for the purposes of the statistical analysis.

Statistical Methods for Secondary Endpoints

The timing of the primary efficacy component failures (incomplete occlusion of the target aneurysm, >50% stenosis of the parent artery at the target IA at 12 months as assessed by angiography, an alternative treatment of the target IA was performed), primary safety components (death or major stroke within 30 days of the implant, death due to a neurological cause, major ipsilateral stroke through 12 months post implant) as well as the secondary endpoint proportions and incidences will be presented using standard summary statistics including the incidence and 95% credible intervals. No hypothesis tests will be performed for the primary or secondary endpoint components or secondary endpoints.

Adverse Events

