 - If the FRED Device cannot be deployed due to any other issues related to the procedure, the Subject will be counted as enrolled but not treated and will not be considered a secondary endpoint failure. The Subject will be maintained within the study for one (1) week. Thereafter, the Subject may be replaced in the study. The Subject will be monitored for any Adverse Event for one (1) week following the failed deployment due to issues related to the procedure. If the Subject has an Adverse Event, that Subject will also have 30-day, 6-month and 12-month clinical follow-ups. An angiographic follow-up will not be required unless the clinician believes it is medically necessary. Unless medically necessary to pursue treatment sooner, it is recommended that further attempts to treat the target aneurysm be deferred for a minimum of one (1) week so that any potential procedural Adverse Events may be monitored.

Subgroup Analysis

Results for the primary and secondary endpoints will be stratified by the following subgroups:

- Location (anterior, posterior)
- Age (<55, 55-64, ≥65)
- Gender: results will be stratified by gender
- Anatomic location (zone 1, 2 and 3)
- Region (Japan, other countries)

Since it is not possible to determine any observed differences are truly due to a difference in treatment effect, any observed significant differences in outcomes ($p < 0.1$) across subgroups will be examined and compared to available literature regarding known risk effects for the subgroups.

Missing Data

In general, all analyses will be performed using the ITT analysis set, which constitutes all available cases and all available visits. Every effort will be made to get 12 month follow-up for all study patients. The primary endpoints will be analyzed first without imputing missing or incomplete data. Multiple sensitivity analyses will be performed in order to better understand the potential effect of missing or incomplete data on the conclusions for the primary endpoints. These sensitivity analyses will impute values for subjects who are event free (for the specific primary endpoint), but do not have complete data. The analysis method used on the imputed datasets will use the binary result (i.e. simple event percents).

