Methods will be endpoint specific. For example, to determine the rate of major strokes, all subjects followed with major strokes reported or no major strokes observed during the defined time period will be counted in the analysis. A lifetable analysis of time to major stroke using the nominal visit will be constructed to use all available data. Other similar endpoints will be analyzed using this strategy.

Other endpoints can be imputed using Expected Mean algorithms. In general, when missing data exists, it is important to assess the impact of missing data on a statistical estimation and testing result; therefore, in addition to analyses based on all observed cases, sensitivity analyses will be performed on the primary endpoints. Multiple imputation method using logistic regression on selected demographic and baseline disease characteristics will be applied.

The best and worst case imputation approach will also be calculated. If under the worst-case approach the study hypotheses are upheld, no further imputation analyses will be performed. Additionally, a multiple imputation approach will be used. We construct a logistic regression model for the probability of failure based on baseline characteristics thought to be predictive of the event and/or of missingness. Imputed datasets will be generated and the results combined to re-test the primary study hypotheses.

Analysis by Center

In this single arm study it is not possible to assess a treatment by center interaction, given there is only one treatment. However, results will be summarized by center for the primary efficacy and safety endpoints. Additionally, an analysis will be performed to assess site homogeneity for these two endpoints.

To facilitate analysis, sites with fewer than 10 subjects may be lumped into a “virtual” or “pseudo” site. If the number of subjects in this pseudo site is large (e.g. greater than 20 subjects), then an attempt will be made to combine the small sites into multiple small sites variables based on geographic location, such that small sites in a similar geographic location are combined but that each pseudo site level created contains at least 10 subjects.

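### SAP 6.6 imputes each subject's likeliest 12-month efficacy outcome without a rule for that judgement, and implies that imputed values count in the primary test, which protocol 6.2 runs first on observed data.

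*SAP*

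**What the plan says.** **SAP 6.6.** It opens with discretion: "efficacy data may be imputed based on subject-specific situations". For subjects missing the 12-month evaluations it then says that "the most likely 12-month efficacy outcomes at the subject-level will be imputed". The inputs named are any available 12-month data and, where occlusion data are missing, 6-month occlusion with pre-treatment data. One group is exempt: "Subjects with no follow-up data will not be imputed for analysis of the primary effectiveness endpoint", although "alternative source-document verified data will be considered in judging 12-month efficacy". If the imputation cannot be made, other subjects' completed outcomes are used to "compute the respective probabilities of 12-month efficacy outcomes conditional on 6 month outcomes".

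**SAP 7.3.** It commits to using 180-day outcomes for subjects without 12-month occlusion data, where 6.6 only permits it. It adds a conditional analysis of 12-month on 180-day outcome, and tipping-point analyses.

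**SAP 6.3 and 7.1.** Section 6.3 computes proportions from non-missing values. Section 7.1 bases the endpoint on core-lab 12-month angiography and uses the posterior Beta(1+E, 1+n−E). Here n counts *evaluable* subjects, a term left undefined. Success requires a posterior probability above 0.95 that the rate exceeds 45%.

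**Protocol 6.2.** "The primary endpoints will be analyzed first without imputing missing or incomplete data". Imputation follows as sensitivity analysis: "in addition to analyses based on all observed cases, sensitivity analyses will be performed on the primary endpoints". This includes best and worst cases and a logistic multiple imputation that re-tests the primary hypotheses.

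**Populations.** Protocol 6.1 limits ITT to subjects with device introduction who were followed for 12 months or failed earlier. SAP 5 includes everyone in whom the device entered the bloodstream.

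**The concern.** Two statisticians could follow this SAP faithfully and report different values of E and n. SAP 6.6 does not say who judges the likeliest outcome, what evidence is enough, or when the judgement cannot be made so that the fallback applies. The fallback yields probabilities, but the posterior needs a count.

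The change in the ITT definition makes this matter more. Under the protocol, a subject without 12-month data who had not failed was outside ITT. Under the SAP that subject is in the primary population, so some rule must decide whether and how the subject counts.

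If singly imputed values do enter the primary test, Beta(1+E, 1+n−E) treats them as observed, because it has no term for imputation uncertainty. In an open-label, single-arm study judged against a fixed threshold, case-by-case decisions could then carry a borderline result across 0.95 in either direction.

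**Working it through.** **1. The plan's own figure.** Inputs from the table in SAP 7.2 (efficacy, original OPC): p0 = 0.45, pA = 0.58, one-sided alpha 0.05, N = 140, stated power 90%. The exact one-sided binomial test rejects at 74/140, with size 3.75% and power 90.6%. The posterior rule of SAP 7.1 rejects at 73/140, with size 5.36% and power 93.1%. The stated power reproduces, so the sample-size arithmetic is not in question.

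**2. Decision bounds.** Find the smallest E with P(π > 0.45 | Beta(1+E, 1+n−E)) > 0.95. N = 145 is the ITT count in SAP 1; 140 is the treated count in SAP 7.2. The numbers missing (7 or 14, about 5% or 10%) are assumptions. With all N counted, the bar is 76/145 or 73/140. If m missing subjects are all entered as successes, the observed cases must supply the bar minus m; if all as failures, the full bar.

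| N | Missing | Observed cases only | All imputed as success | All imputed as failure |
|---|---|---|---|---|
| 145 | 7 | 72/138 (52.2%) | 69/138 (50.0%) | 76/138 (55.1%) |
| 145 | 14 | 69/131 (52.7%) | 62/131 (47.3%) | 76/131 (58.0%) |
| 140 | 7 | 70/133 (52.6%) | 66/133 (49.6%) | 73/133 (54.9%) |
| 140 | 14 | 66/126 (52.4%) | 59/126 (46.8%) | 73/126 (57.9%) |

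The last two columns are extremes, not forecasts. A near miss shows the mechanism: 68/131 has posterior 0.944 and fails, but if 8 of 14 missing subjects are judged successes it becomes 76/145, posterior 0.963, and passes.

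**3. False-positive rate under one mechanical reading.** Take the true 12-month rate as 45%, data missing at random, and each missing outcome set to the subject's 180-day status (one reading of SAP 7.3). Then E = Binomial(N−m, 0.45) + Binomial(m, q), where q is the assumed 180-day success rate. Reject at E ≥ 76 (N = 145) or E ≥ 73 (N = 140).

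| N | Missing | q = 30% | q = 45% | q = 55% | Observed cases |
|---|---|---|---|---|---|
| 145 | 7 | 3.0% | 4.4% | 5.6% | 5.4% |
| 145 | 14 | 1.9% | 4.4% | 7.0% | 4.7% |
| 140 | 7 | 3.6% | 5.4% | 6.8% | 4.7% |
| 140 | 14 | 2.4% | 5.4% | 8.5% | 5.8% |

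**4. Readings of SAP 6.6 itself.** In 200,000 simulated trials with 14 of 145 missing, transition rates were estimated from observed cases.

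| Assumed 180-day success, share still successful at 12 months | Likeliest value | Expected count | Expected count, rounded |
|---|---|---|---|
| 30%, 90% | 1.9% | 5.7% | 5.0% |
| 55%, 75% | 7.0% | 5.6% | 4.9% |

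The same text thus supports procedures with different error rates, and their order changes with the assumptions.

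**The case against.** The strongest reply is that the plan has more structure than a bare judgement. SAP 6.6 can be read as separate routes: the likeliest-outcome step for subjects missing all three 12-month evaluations, 6-month occlusion for those lacking only occlusion data, and the conditional probabilities as fallback. SAP 7.3 names the 180-day source without hedging. The 180-day angiograms are read by independent, blinded core-lab reviewers (protocol 12.1.1), the SAP is to be approved before outcomes are analysed (SAP 9.4), and tipping-point analyses are planned. Much of this stands. A reader might infer that the SAP has no rule for missing efficacy data at all, and the documents do not support that. What is missing is a rule for the first-line step and for turning a probability into E. Blinded reading of the 180-day angiogram does not supply one, because the core lab is not assigned the imputation. Approving the SAP early does not help when the approved text defers the decision to individual cases.

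A reader might also infer that the SAP plans to decide success on judged outcomes. It does not say so. That imputed values enter the primary test is implied by one exemption in 6.6, while SAP 6.3, the wording of SAP 7.1 and protocol 6.2 point to observed data.

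Finally, the error rates come from mechanical rules and assumed missingness, so they do not measure the effect of free judgement. With 7 of 145 missing, the highest is 5.6% against 5.4% for observed cases. That limit stands.

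**Conclusion.** The concern holds as an unresolved choice that should be fixed before analysis. The SAP does not fix E and n for the primary efficacy test, and 6.6, 7.3, SAP 5 and the protocol's ITT definition and missing-data section do not agree.

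The size depends on quantities that the documents do not give. With 14 of 145 assumed missing, the false-positive rate under 180-day carry-forward runs from 1.9% to 7.0%, against 4.7% for observed cases. With 7 missing it runs from 3.0% to 5.6%, against 5.4%. These rates rest on data missing at random, a true rate of 45% and 180-day success of 30% to 55%.

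A reader might infer a bias towards the device. The calculations do not support that: several scenarios are more conservative than the observed-case test, and the effect is small if few data are missing. The tipping-point analysis would expose a fragile result, but it does not say which analysis decides success.

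**What to change.** - Delete the subject-level likeliest-outcome rule from SAP 6.6.
- State that the observed-case analysis decides primary success. This is consistent with the order in protocol 6.2, although the protocol puts that analysis first without calling it decisive.
- Reconcile the ITT definitions in protocol 6.1 and SAP 5. Define *evaluable* as ITT subjects with a core-lab 12-month angiogram plus known earlier failures, following protocol 6.2, which counts a subject as failing if "A retreatment of the target aneurysm is required at any time prior to the 12-month follow-up evaluation".
- Fix one rule for deaths before 12 months, before outcomes are seen.
- Merge SAP 6.6 and 7.3 into one algorithmic sensitivity analysis: Beta(1,1) priors on 12-month success given 180-day success and given 180-day failure, with missing outcomes drawn within the posterior. Say whether it replaces or accompanies the protocol's logistic multiple imputation. At a true rate of 45% and N = 145, 6,000 simulated trials per case gave false-positive rates of 4.5% to 5.1% (7 missing) and 4.9% to 5.2% (14 missing), with Monte Carlo error of about 0.3 points.
- Keep the tipping-point analysis for subjects with no 180-day result, with the protocol's best and worst cases as its two ends.

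The cost is SAP wording and a few lines of code; no new data are needed. Because the posterior variance is proportional to 1/(n+3) at a given rate, the credible interval is wider than when imputed values count as data by √(148/141) = 1.02 with 7 missing and √(148/134) = 1.05 with 14, or about 2% to 5%. Keeping early failures while omitting event-free dropouts also leans somewhat against the device; the sensitivity analysis will show by how much.

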A supplement analysis was also conducted to identify the in-stent stenosis rate (3.8%) to ensure that this event is not underreported across multiple publications. A 12% core lab adjustment was added when calculating the OPC for publications which did not include a core lab when reporting on aneurysm occlusion. The combined estimate for effectiveness for the anterior circulation (15 articles) was 56.2% (95% CI 42.8, 69.6) leading to a 45% one-sided lower 95% confidence limit for the anterior location. The combined estimate for effectiveness for the posterior location (9 articles) was 40.1% (95% CI 17.8, 62.3) leading to a 21.4% one-sided lower 95% confidence

limit for the posterior location. The sample size for the anterior circulation was 1120 vs. 81 for the posterior circulation.

Study Differences:

The current study will assess both anterior and posterior lesions following treatment. The combined anterior and posterior OPC from the FRED literature analysis document for both safety and efficacy is not directly comparable to that used for Pipeline since the PED was only used to treat ICA segments up to the superior hypophyseal segment whereas the FRED target is multiple vessel segments in the anterior and posterior circulation. The FRED study expects to up to 80% in the anterior circulation and up to 20% in the posterior circulation.

The Pipeline PUFs Study had a different primary safety endpoint which was the proportion of subjects who experienced either death due to neurologic causes or major ipsilateral stroke by 180 days after the last IA treatment procedure whereas the FRED Study primary safety endpoint is the proportion of subjects who experience one or more of the following: death or major stroke within 30 days post procedure and neurological death or major ipsilateral stroke within 12 months post procedure. Thus the primary safety endpoints are different. The 20% OPC used in the PUFs Study is likely too low given the longer duration.

OPC Selection Criteria:

The OPC for efficacy is motivated by our literature analysis where a 45% OPC was estimated to be the 95% lower bound determined from a series of qualifying publications. This estimate was based on a mixture of anterior and posterior lesions.

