2. Proportion of subjects in whom an alternative treatment of the target IA had not been performed within 12 months
3. Proportions of subjects with clinically acceptable aneurysm occlusion (90 %-100 %) of the target aneurysm at 12 months (+ 60 days, -30 days)
4. Incidence of $\geq 50\%$ In-Stent Stenosis(ISS)at the target IA at 12 months as assessed by angiography at an independent corelab

5. Proportion of subjects with complete occlusion of the target aneurysm on 12-month angiography(+ 60 days, -30 days)
6. Incidence of FRED System procedure related Serious Adverse Events
7. Incidence of FRED System device related Serious Adverse Events;
8. Incidence of unsuccessful delivery of the FRED device
9. Incidence of unsuccessful deployment of the FRED device
10. Incidence of migration of the FRED device at 12 months
11. Unplanned alternative treatment on the target IA within 12 months defined as re-treatment of the target aneurysm with an alternative treatment modality including open repair, endovascular placement of an additional stent or treatment of In-stent Stenosis observed at the 180 day or 12 month follow-up time-points or at an unscheduled study follow up visit.
12. Incidence of change in clinical and functional outcomes at 180 days and 1 year follow up, as measured by an ≥ 3 point increase in the modified Rankin Scale due to neurologic disability as compared to baseline
13. Incidence of major stroke, as measured by NIHSS at 12-months (and ophthalmic examination related to the target aneurysm if determined appropriate)
14. Incidence of minor stroke, as measured by NIHSS at 12-months (and ophthalmic examination related to the target aneurysm if determined appropriate)

The statistical analyses of the primary and secondary endpoints of the study will be based on imaging data that has been reviewed and assessed by an independent core lab and on trial clinical data that has been reviewed and adjudicated by the independent Clinical Events Committee (CEC).

Study Success Criteria:

The criterion for success is based on the posterior probability of the alternative hypotheses for both efficacy and safety (i.e. both efficacy and safety being met).

Efficacy Criterion

The FRED System will be declared efficacious if the posterior probability of the alternative hypothesis H_A based on the primary efficacy endpoint for is large, that is

$$P(H_A|Data) = P(\pi_e > 45\%|Data) > \pi^*$$

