4.3 FINAL ANALYSES

Final statistical analyses will be performed as detailed below.

Two OPC sets will be considered in support of efficacy and safety as per the original protocol as well as more restrictive OPCs as follows:

- Primary: Original PG specified in the protocol (45% for efficacy and 25% for safety)
- Supportive: Updated PG presented to FDA at the Feb 2017 meeting (46% for efficacy and 15% for Safety).

Primary Analyses: The powers will be 80% to rule out a 45% OPC (efficacy) margin (lower bound) and 80% to rule out a 25% OPC (safety) margin (upper bound) using one-sided tests. The trial will be considered successful if the one-sided 95% credible lower bound of the efficacy rate exceeds the 45% OPC and the one-sided 95% credible upper bound of the safety rate is below the 25% OPC. The use of one-sided testing is consistent with the original protocol.

Supportive Analyses: The powers will be 90% to rule out a 46% OPC (efficacy) margin (lower bound) and 90% to rule out a 15% OPC (safety) margin (upper bound) using two-sided tests. The trial will be considered successful if the two-sided 95% credible lower bound of the efficacy rate exceeds the 46% OPC and the two-sided 95% credible upper bound of the safety rate is below the 15% OPC. The use of two-sided testing is consistent with the PIPELINE PMA and FDA guidance.

Study success is defined as achieving statistical significance for the primary OPCs.

Thus, both one-sided and two-sided credible intervals will be computed for the primary (one-sided) and supportive (two-sided) analyses. However, since the success standards are higher for both safety and efficacy for the supportive analyses than for the primary analyses, credible interval claims in support of labeling will be sought based on the more restrictive supportive analyses which are nested within the alternative hypotheses.

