7 ENDPOINT ANALYSES

7.1 PRIMARY EFFICACY VARIABLE

The primary efficacy endpoint is the percent of subjects in the ITT population with complete occlusion (defined as Raymond class I) without clinically significant stenosis (defined as $\geq 50\%$ stenosis) of the parent artery at the target IA based on core lab evaluations at the 12-month follow-up angiography and in whom an alternative treatment of the target IA had not been performed post-FRED placement. An alternative treatment is defined as re-treatment of the target aneurysm with an alternative treatment modality including open repair, endovascular

placement of an additional stent or treatment of In-stent Stenosis observed at the 180-day or 12 month follow-up time-points or at an unscheduled study follow up visit.

The primary efficacy hypotheses are:

$$H_{E0}: \pi_E \leq 0.45$$

$$H_{E1}: \pi_E > 0.45$$

The null hypothesis (H_{E0}) for this endpoint states that the true proportion of subjects treated with the FRED Device who achieve complete occlusion (Raymond class I) without clinically significant ($\geq 50\%$) stenosis of the parent artery 12 months post-treatment and without any subsequent alternative treatment is no higher than 45%. The alternative hypothesis the FRED trial aims to demonstrate is that the true proportion of subjects who achieve effectiveness success at 12 months is greater than 45%.

Using the prior

$$\pi_E \sim Beta(1,1)$$

the posterior distribution for the primary efficacy endpoint rate will be

$$\pi_E | E, n \sim Beta(1 + E, 1 + n - E)$$

where n is the number of evaluable subjects and E is the number of subjects who meet the efficacy endpoint. The point estimate of the posterior distribution of the primary efficacy endpoint will be presented with its lower 95% credible bound, as well as the posterior probability of the alternative hypothesis H_{E1} . If the posterior probability exceeds 0.95, the primary efficacy endpoint will have been met.

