7.2 PRIMARY SAFETY ENDPOINT

The study's primary safety endpoint is the proportion of subjects in the Safety Population who experience either major stroke or death within 30 days, or major ipsilateral stroke or neurological death 31 days through 12 months post procedure. CEC-adjudicated data will be used for this analysis.

The primary safety hypotheses are:

$$H_{S0}: \pi_S \geq 0.25$$

$$H_{S1}: \pi_S < 0.25$$

The null hypothesis (H_{S0}) for this endpoint states that the true proportion of subjects treated with the FRED Device who experience neurologic death or major ipsilateral stroke one-year post-treatment is equal to or higher than 25%. The alternative hypothesis the FRED trial aims to demonstrate is that the true proportion of subjects treated with the FRED Device who experience neurologic death or major ipsilateral stroke one-year post-treatment is actually lower than 25%.

Using the noninformative prior

$$\pi_S \sim \text{Beta}(1,1)$$

the posterior distribution for the primary safety endpoint event rate will be

$$\pi_S | S, n \sim \text{Beta}(1 + S, 1 + n - S)$$

where n is the number of evaluable subjects and S is the number of subjects who meet the safety endpoint. The point estimate of the posterior distribution of the primary safety endpoint will be presented with its lower 95% credible bound, as well as the posterior probability of the alternative hypothesis H_{S1} . If the posterior probability exceeds 0.95, the primary safety endpoint will have been met

The supportive analysis (second OPC set) will be conducted for both primary efficacy and primary safety using more restrictive performance goals identified from a revised set of literature analysis and presented to FDA on 16 February 2017. The format of this analysis will be a Bayesian design identical in form to the above except that the performance goals will be 0.46 for efficacy and 0.15 for safety. Details of the resulting analyses and associated power are as below, from which it can be seen that the study is sufficiently powered at the final enrolled and treated count of 140.

	Efficacy		Safety	
	Original	Revised	Original	Revised
Significance level, alpha	0.05	0.025	0.05	0.025
1 or 2-sided test	1	1	1	1
Null: OPC, p_0	0.45	0.46	0.25	0.15
Alternative: FRED, p_A	0.58	0.60	0.15	0.06
Power (%)	90	90	90	92
N	140	140	140	140

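### For subjects with no follow-up data, SAP 6.6 admits source-document evidence on 12-month primary efficacy without requiring a core-lab read, in conflict with SAP 7.1 and protocol 5.5

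*SAP*

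**What the plan says.** SAP 6.6 (Missing Data Imputations) has several routes for an absent 12-month result. The one at issue is its last rule for primary efficacy: "Subjects with no follow-up data will not be imputed for analysis of the primary effectiveness endpoint", followed in the same sentence by the provision that "alternative source-document verified data will be considered in judging 12-month efficacy". The section does not say what counts as such data, who makes the judgement, or whether any images must go to the core lab.

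Other sections fix the basis of the endpoint:

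- SAP 7.1 defines primary efficacy as "based on core lab evaluations at the 12-month follow-up angiography".
- Protocol 5.5 says the primary and secondary analyses will be "based on imaging data that has been reviewed and assessed by an independent core lab".
- Protocol 12.0 makes occlusion status and parent artery patency the core lab's task, and protocol 12.1.1 requires independent, blinded reviewers.
- SAP 7.4 relies on central adjudication and the independent core lab when it argues that results are consistent across sites.

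Protocol 5.1 reports on the literature behind the efficacy goal: "A 12% core lab adjustment was added when calculating the OPC for publications which did not include a core lab".

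**The concern.** This is a single-arm study judged against a fixed goal, so the way success is ascertained is part of the comparison. A judgement from site records is not the blinded central read on which the endpoint is defined. SAP 6.6 opens that route for the subjects with the least trial evidence and sets no limit on the evidence or on who weighs it.

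The adjustment in protocol 5.1 shows that the sponsor regarded core-lab status as material when it derived the goal.

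There is a second consequence. The tipping-point analysis in SAP 7.3 covers subjects without a primary endpoint. A subject already judged a success from source documents has an endpoint, and could drop out of the analysis meant to test dependence on missing data.

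**Working it through.** **Inputs from the documents**

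- Goal p0 = 0.45 (SAP 4.3).
- Rule: Beta(1,1) prior, success if the posterior probability that the rate exceeds 0.45 is above 0.95 (SAP 7.1).
- ITT cohort n = 145 (SAP 1, Study Design).
- Power table: N = 140, p0 = 0.45, assumed rate 0.58, one-sided alpha 0.05, power 90% (SAP 7.2).

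**Assumptions**

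- m, the number of subjects judged on source documents. The documents do not give it.
- q, the probability that such a subject is called a success when the true core-lab rate is 45%. Protocol 5.1 does not say whether its 12% is absolute or relative, so both are shown: q = 0.45 + 0.12 = 0.57, and q = 0.45 × 1.12 = 0.504. Both assume that source-document judgements err upward, which the protocol does not state. The limiting case is q = 1.

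**Step 1: the plan's own figure.** The exact binomial test at N = 140 needs at least 74 successes. P(X ≥ 74) is 3.75% at a rate of 0.45 and 90.6% at 0.58, so the stated 90% is reproduced. The planned Bayesian rule needs 73 of 140, with a type I error of 5.36% and power of 93.1%.

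**Step 2: threshold at n = 145.** The smallest y for which P(π > 0.45 | Beta(1 + y, 146 − y)) exceeds 0.95 is y = 76 (posterior probability 0.963; at 75 it is 0.948). With a core-lab read on everyone, P(Binomial(145, 0.45) ≥ 76) = 4.4%.

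**Step 3: m subjects judged on source documents.** The false-success rate is P(A + B ≥ 76), with A ~ Binomial(145 − m, 0.45) and B ~ Binomial(m, q), computed exactly by convolution.

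| m | q = 0.57 | q = 0.504 | q = 1 |
|---|---|---|---|
| 0 | 4.4% | 4.4% | 4.4% |
| 3 | 5.0% | 4.6% | 7.4% |
| 5 | 5.4% | 4.8% | 10.2% |
| 10 | 6.6% | 5.3% | 20.5% |

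The bias in the expected success rate is m(q − 0.45)/145. At q = 0.57 this is 5 × 0.12/145 = 0.4 points for m = 5, and 10 × 0.12/145 = 0.8 points for m = 10.

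**Step 4: comparison with the repaired rule.** If the m subjects leave the evaluable set, n becomes 145 − m and the threshold changes.

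| m | Current text, q = 0.57 | Subjects excluded | Threshold when excluded |
|---|---|---|---|
| 5 | 5.39% | 5.36% | 73 of 140 |
| 10 | 6.6% | 4.6% | 71 of 135 |

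At m = 5 the two rules hardly differ, because the discreteness of the binomial is as large as the assumed bias.

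**The case against.** The strongest reply is that SAP 6.6 should be read with the rest of the plan. It never says that the data bypass the core lab, and it says only that they will be considered. SAP 7.1, SAP 7.4, protocol 5.5 and protocol 12.0 all make the core lab the source of the imaging result. On that reading, outside images would be sent to the core lab, or source documents would serve only for non-imaging facts such as retreatment. This is a possible intention, but SAP 6.6 does not state it. Its wording gives a route to judging the primary outcome with no such condition.

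The objection on size stands. The clause reaches only subjects with no follow-up data who also have verifiable 12-month evidence from elsewhere. Subjects with 180-day data follow other rules.

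Three stronger readings are tempting, and the documents do not support them:

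- **That local readings will decide the primary result.** The text is silent on who reads the images, and it confines the clause to subjects with no follow-up data.
- **That the protocol discounts readings made without a core lab by 12%.** Protocol 5.1 says an adjustment was added for certain publications. It gives neither direction nor scale, and it concerns literature, not trial subjects. A downward correction is plausible but is an inference.
- **That the 20% attrition allowance in protocol 6.2 sizes the problem.** Applied to 145 it gives 29 subjects and a false-success rate of 12.9% at q = 0.57. But that allowance covers all loss through 12 months. It does not count subjects with no follow-up data who are then judged on outside evidence.

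**Conclusion.** The conflict is real: SAP 6.6 permits a judgement of 12-month primary efficacy without the core-lab read on which SAP 7.1 and protocol 5.5 rest the endpoint. Severity is minor to moderate.

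With five to ten affected subjects and judgements 12 points high, the false-success rate moves from 4.4% to between 5.4% and 6.6%. If the 12% is relative, it moves to between 4.8% and 5.3%. A larger effect needs selectively favourable judgements, as in the limiting case where every such subject is called a success. The clause contains nothing to exclude this, and nothing to suggest it is intended. These figures rest on the assumed number of subjects and on an upward error, neither of which the documents give. The case for a change rests on the contradiction and the open discretion more than on the expected size.

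**What to change.** Amend SAP 6.6 before outcomes are analysed:

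1. The occlusion and stenosis components of the primary endpoint come only from angiograms read by the existing core lab. Outside or unscheduled angiograms are forwarded to it.
2. Documented retreatment of the target aneurysm remains a failure, as protocol 6.2 already defines, whatever imaging exists.
3. Any other subject without a core-lab read is treated as missing and enters the tipping-point analysis of SAP 7.3.
4. The number of subjects affected is reported.

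The rule treats images that suggest success and images that suggest failure alike. Only retreatment, which needs no imaging, counts without a core-lab read. The cost is a short text change and the forwarding of a few image sets. The downside is that a few subjects may move to missing.
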